Annual assessments of new literature in the field that may have an impact on the safety of participants or on the ethics for the research study will be conducted by the graduate student research assistant under the oversight of the PI and Co-Is. The PI and Co-Is will evaluate this new information for its bearing on all aspects of this research project. This information and the team’s analysis will be disseminated to the SMC at least annually, or sooner if important external factors or relevant information is identified that impacts subject safety or raises ethical concerns. In addition, at each committee meeting, SMC members also will be queried about new studies or ethical issues that they think should be discussed or reviewed, and these items put on the SMC meeting agenda.

f. Advanced Plans for Interim or Futility Analysis

This research project compares the psychological and physical outcomes of Resourcefulness Training against Attention Control in parents caring for technology-dependent children at home. The study investigators anticipate a medium effect size for these interventions; given this expectation and the low risk nature of the study, no formal “futility analysis” will be conducted. However, data summaries will be reviewed by the SMC every six months and interim analyses will be conducted as recommended by the SMC.

Drugs or Devices

There are no drugs or devices being utilized in this research project – *please leave rest of this section blank*

1. *If the research involves drugs or device(s), describe your plans to store, handle, and administer those drugs or device(s) so that they will be used only on research participants and be used only by authorized investigators.*
2. *How will the drug(s) be dispensed (i.e., indicate the pharmacy that will be used)?*
3. *If the drug is investigational (has an IND) or the device has an IDE or a claim of abbreviated IDE (non-significant risk device), identify the holder of the IND/IDE/Abbreviated IDE*

Additional Information

If you have any additional information regarding your study not covered in the template, please include it here.

Community-Based Participatory Research

- This is not a community-based participatory research project – *please leave rest of this section blank*

If applicable, describe the involvement of the community in the design and conduct of the research.

Note: Community based research is research that is conducted as an equal partnership between academic investigators and members of a community. In Community Based Participatory Research (CBPR) protects, the community participates fully in all aspects of the research process.

International information

- This is not an international study – *please leave rest of the section blank*
- We will be conducting this research at the following international sites:
 - 1.
- We are recruiting participants outside of the US from the following locations:
 - 1.
- We are sending data outside of the US to the following locations:
 - 1.
- We are receiving data from outside of the US from the following locations:
 - 1.

MULTI-SITE RESEARCH (when UH or CWRU is the IRB of Record)

Does this project have multiple sites?

- Yes**
- No**

The Cleveland Clinic Children’s Hospital (Pulmonary, Gastroenterology, Neurology sections) are only inviting their patient’s parents to participate in the study. If the parent is interested they complete a form giving their contact information that the CC team sends to us via secure email.

Non-Local Site Information for Multi-Site Studies

If this is a multi-site study where you are the lead investigator, list the following information for each relying site:

1. Name of site:

2. PI of relying site:
3. Name of IRB contact:
4. Phone number of IRB contact:
5. Email address of IRB contact:

Non-Local Recruitment Methods for Multi-Site Studies

*If this is a multi-site study and research participants will be recruited by methods **not under the control of the local site** (e.g. call centers, national advertisements) describe those methods.*

Local recruitment methods are described above.

1. *Describe when, where, and how potential research participants will be recruited.*
2. *Describe the methods that will be used to identify potential research participants.*
3. *Describe the materials that will be used to recruit research participants.*

Above Not Applicable.

Multi-Site Research Communication Plan (when you are the lead investigator)

Not applicable

*If this is a multi-site study where you are the **lead investigator**, describe the processes to ensure communication among sites including:*

- *All sites will have the most current version of the protocol, consent document, and HIPAA authorization*

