Research Design. A quasi-experimental RCT design with random assignment will be used to test the efficacy of a Resourcefulness Training (RT) intervention compared with an attention control group in mothers and fathers of technology-dependent children. All participants will receive a face-to-face visit from study staff for the T1 data collection. In addition, the intervention group will receive individually tailored RT web based instruction via an approximately 30 minute video that provides details on each of the 8 resourcefulness skills with short examples of application, instruction on journal writing to practice and reinforce use of resourcefulness skills, access to video tapes of parents describing application of resourcefulness skills in the care of their technology-dependent child. Parents will be asked to provide their email address so that we may send them invitation for access to the website that they may visit at any time to access the video tapes. Data will also be collected face-to-face at 3 months (T3) and 6 months (T4) post-intervention. At 6 weeks parents will be emailed a link to the REDCap survey for Time 2 data collection and contacted by phone for SF-12 survey with email reminders. Open-ended questions following their final data collection appointment will allow mothers/fathers to discuss feasibility, acceptability, and fidelity of this intervention and suggestions for potential modification of the intervention and follow up procedures. For this study, 99 female participants and 24 male participants are expected to be enrolled that takes into account 10% attrition.

Measures/Instruments.

The **Depressive Cognition Scale** an 8-item scale ($\alpha = .75$), will measure depressive thought patterns that may lead to depression.⁸ Responses on a 6-point scale range from strongly agree (5) to strongly disagree (0) with a score range 0-40. Items include depressive cognitions such as hopelessness and worthlessness; higher scores indicate more depressive cognitions.

The **Resourcefulness Scale**, a 28-item scale ($\alpha = .85$), will assess both personal (16 items) and social (12 items) resourcefulness.⁹ Responses on a 6-point scale range from extremely descriptive (5) to not descriptive (0) with a score range 0-140; higher scores indicate greater resourcefulness. Construct validity was assessed using confirmatory factor analysis.

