Variable	Measure (Appendix A)	Time of measure				Reliability in previous studies		
Outcome Variables: Parent		Enroll 6 Wk						
		3M	6M					
Psychological and Physical Health	Medical Outcomes Short Form Health Survey (SF-12 version 2)	X	X	X	X	$\alpha=.85-.93$		
Depressive Cognitions	Depressive Cognition Scale	X	X	X	X	$\alpha=.75-.93$		
Depressive Symptoms	Center of Epidemiological Studies- Depression Scale (CES-D)	X	X	X	X	$\alpha=.84-.93$		
Stress	Pediatric Inventory for Parents (PIP)- subjective Hair Cortisol- objective	X	X	X	X	$\alpha=.80-.96$		
		X		X	X	Sensitivity/Specificity=100%		
Burden	Zarit Burden Interview-12	X	X	X	X	$\alpha=.85-.89$		
Outcome Variable: Family		Enroll 6 Wk						
		3M	6M					
Family Functioning	Feetham Family Functioning Survey	X	X	X	X	$\alpha=.73-.83$		
Mediating Variable		Enroll 6 Wk 3M 6M						
Resourcefulness: Personal	Resourcefulness Scale (Personal Resourcefulness Subscale)	X	X	X	X	$\alpha=.83$		
Resourcefulness: Social	Resourcefulness Scale (Social Resourcefulness Subscale)	X	X	X	X	$\alpha=.79$		
Covariates		Enroll 6 Wk 3M 6M						
Parent: · Race/Ethnicity, Gender, Family Income		Enrollment form		X		IRR=1.0		
Technology-Dependent Child: · Functional Status		Functional Status II- Revised		X	X	X	X	$\alpha=.76-.80$
Sample Characteristics		Enroll 6 Wk 3M 6M						
Parent: · Age, Marital Status, Duration of Tech. Dependent Child Caregiver Role		Enrollment form		X			IRR=1.0	
· Education, Amount of Home Nursing Support Services, Lay Caregiving Assistance		Enrollment form		X	X	X	X	IRR=1.0
· Interpersonal Support		Interpersonal Support Evaluation List		X	X	X	X	$\alpha=.88-.90$
Technology-Dependent Child:								

Age	Enrollment form	X				IRR=1.0
Type of Medical Technology Used	Technology Dependency Questionnaire	X	X	X	X	NA

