After confirming the child's assent and obtaining the participant's written informed consent, the participant will be assigned a code number. Mothers/fathers will be randomly assigned to one of two treatment conditions- Resourcefulness Training intervention or Attention Control using the Minim computerized method of random assignment based on parent gender, child's type of technology (mechanical ventilation or intravenous medication/nutrition, all others), race ethnicity (White non-Hispanic, all others). Data collection will take place in a private place of the mother's/father's choosing such as her/his home. The instruments should take about 50 minutes to complete at initial enrollment but thereafter it should take about 30 minutes (Table 1). After the participant has completed the self administered questionnaires, the interviewer will score the CES-D. If the total score of the CES-D exceeds the cutoff of 16 for depressive symptoms the participant will be notified and the information regarding mental health resources will be given-(see additional files). Following T1 data collection, mothers/fathers will receive either intervention or attention control protocol according to their random assignment. The RT intervention which includes instruction on maintaining a 28 day journal will take about 45-50 minutes to review with participants. At T4, one additional questionnaire, Resourcefulness Skills Scale, will be given to the Resourcefulness Training intervention group only to assess for intervention fidelity. Reminder post cards will be sent as needed. A \$25 gift card will be given following completion of questionnaires at each of four time points. Following completion and submission of all questionnaires and the RT journals, participants will be interviewed via speaker phone to determine the feasibility, acceptability and fidelity of the intervention. Telephone interviews will take place at a time convenient for the participant and will be audio-recorded. In order to aid in retention, participants will be mailed birthday cards on the parent's and child's birthdays as well as monthly postcards with an inspirational message and contact information for the study office. The **RT intervention** group will be taught RT skills and mnemonic strategies (acronyms, practice) to facilitate recall of RT skills using a web based program that includes a video approximately 32 minutes long. The 8 letters in the acronym **RESOURCE** will be used to prompt recall: **R**ely on family/friends; **E**xchange ideas with others; **S**eek professionals or experts; **O**rganize daily activities; **U**se positive self-talk; **R**eframe the situation positively; **C**hange from usual reaction; **E**xplore new ideas. Practice of RT will occur through using a personal semi-structured journal (example in other study documents) to daily record which resourcefulness skills were used that day as well as one's thoughts and feelings related to specific situations in which the resourcefulness skills were used. As intervention reminder tools mothers/fathers will be given a laminated card to keep in their journal as well as a magnet to

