answer the interview and study questions. Parents will be told that they may choose to take a break at any point during the interview. The amount of time required for participation in the study may also be viewed as an inconvenience. A potential emotional risk during the interview is that recalling information regarding their child’s course of illness and home management difficulties may make some parents uncomfortable. Participants will be told that they may withdraw from the study at any time. The interviewer will be vigilant to assess the participant’s discomfort. Participants experiencing considerable discomfort will be asked if they wish to stop the interview and will be given supportive assistance by the interviewer. The mother/father will then be given the number of United Way First Call (211) to access on call mental health professional services in their local area or Cuyahoga County 24-Hour Mental Health Crisis Information and Referral [contact]). If any participant is noted to have a level of depressive symptoms above the recognized cutoff of 16 on the Center for Epidemiological Studies (CES-D) measure she/he will be told of the findings and given an information sheet regarding accessing mental health care resources such as United Way First Help (phone 211) or the Cuyahoga County 24-Hour Mental Health Crisis Information and Referral [contact]). Any participant noted to have a score of 23 or above on the CES-D will be assessed for imminent risk of suicide by asking if they have had any thoughts of harming themselves in any way or perhaps killing themselves. If the answer to any portion of the question is “yes” the participant will be told of a concern for their safety and the necessity for the interviewer to contact the Mobile Crisis Team from the Cuyahoga County 24-Hour Mental Health Crisis, Information and Referral Hotline immediately. The risks and discomforts involved are reasonable because the risks are temporary and can be minimized by the above procedures. In addition, the discomfort is no more than what the participant might experience in her/his daily life.

**3. Describe: Procedures to decrease risk- See above
Drugs/Devices; Source Records- Not Applicable**

- Procedures performed to lessen the probability or magnitude of risks*

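### The 6-week CES-D arrives by emailed link, but the plan does not say who scores it, when, or how the parent is reached, so a high score can go unseen until 3 months

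*Combined protocol and SAP*

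**What the plan says.** Four places in the combined protocol and SAP bear on this.

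- **Schedule.** Table 1 (Study Tools and Measures) marks the CES-D at enrolment, 6 weeks, 3 months and 6 months.
- **Mode of collection.** Under Study Design, Procedures and Timeline, the Research Design paragraph makes T1 a face-to-face visit and says of the last two assessments: "Data will also be collected face-to-face at 3 months (T3) and 6 months (T4) post-intervention". For T2 it says: "At 6 weeks parents will be emailed a link to the REDCap survey for Time 2 data collection". The same sentence adds that parents will be "contacted by phone for SF-12 survey with email reminders".
- **Scoring and notification.** The procedures text after Table 1 says: "After the participant has completed the self administered questionnaires, the interviewer will score the CES-D". It continues: "If the total score of the CES-D exceeds the cutoff of 16 for depressive symptoms the participant will be notified", and information on mental health resources is then given.
- **Higher scores.** Item 2 of the same section, repeated under Risks to Research Participants, says: "Any participant noted to have a score of 23 or above on the CES-D will be assessed for imminent risk of suicide". The assessment is a question about thoughts of self-harm. If the answer is yes, the parent is told of "the necessity for the interviewer to contact the Mobile Crisis Team", and this is to happen at once.

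**The concern.** The safety procedure is written for an encounter: the parent completes the forms, an interviewer scores one of them, and the interviewer speaks to the parent about the result. T1, T3 and T4 fit that pattern. T2 does not, because the CES-D goes into an online survey that the parent completes alone.

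The plan requires action on scores above 16 and further action at 23 or above, but at one of its four assessments it gives no route from the completed form to a person who will act on it. At stake is a parent who submits a score at a level the plan itself says needs follow-up, with no one assigned to read it. This is a matter of participant safety. It has no bearing on power or on the estimate of the intervention effect.

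**Working it through.** The plan states no figure to reproduce here. The check sets the passages side by side, followed by a rough count for scale.

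**1. Is the CES-D part of T2?** Yes. Table 1 marks it at 6 weeks.

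**2. By what mode?** The Research Design paragraph offers two T2 channels, the REDCap link and the phone. It names only the SF-12 for the phone, so the CES-D falls to the link.

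**3. Who scores it?** The procedures text names the interviewer. It can be read in two ways:
- If it covers T1 only (the text soon moves on to what follows T1 data collection), T2 has no scoring step.
- If it covers every time point, it relies on an interviewer to whom the T2 plan gives no CES-D task.

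Either way, the person and the timing are unstated for T2.

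**4. Does another planned contact close the gap?**

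| Contact | Where described | Closes the gap? |
|---|---|---|
| SF-12 call at T2 | Research Design | No. It is not timed after the online survey or linked to its score; a parent could be phoned first and submit later. |
| Weekly calls | Objectives; procedures text | No. They run for four weeks and end before T2. |
| Calls at 2 months | Booster paragraph | No. They cover skills (intervention arm) or general wellbeing and appointments (control arm), not CES-D results. |
| Staff usually available within 24 hours | Adverse and Unanticipated Events | No. This applies when a parent expresses distress or asks for help. |

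**5. How long could a score stay unread?** The next CES-D with an interviewer present is at 3 months. Taking 3 months as 12 to 13 weeks, the interval is 12 − 6 = 6 to 13 − 6 = 7 weeks.

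**6. Scale.** Inputs: 99 + 24 = 123 enrolled and 10% attrition (Research Design); 39.2% scoring 16 or more among 103 mothers (Background). Assumption: that rate applies to this sample at 6 weeks.

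- Parents remaining: 123 × (1 − 0.10) = 110.7, about 111.
- Expected at 16 or more: 110.7 × 0.392 = 43.4, about 43.
- If the rate were 25% or 50% (an assumed range): 110.7 × 0.25 = 27.7 and 110.7 × 0.50 = 55.4, so about 28 to 55.
- On the 94 parents named in the Objectives: 94 × 0.392 = 36.8, about 37.

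No corresponding count can be given for 23 or above, because the documents report neither a rate at that level nor a distribution of scores.

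**The case against.** The strongest reply is that the procedure already reaches T2. The rule for 23 or above covers any participant and is not limited by visit or mode. Its steps are asking a question, giving information and calling a crisis service, and none is said to need physical presence. A live call to each parent is planned at T2, so staff could score the survey and use that call.

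Much of this stands, and it rules out some stronger readings that a reader might infer:

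- **That nobody is in contact with parents at T2.** The SF-12 call shows otherwise. What is missing is a link between that call and the CES-D.
- **That the procedure cannot operate at T2.** The text does not say so. It leaves out the mechanism and the timing, and staff might supply both.
- **That high T2 scores will be missed.** The documents support only that they can be.
- **That some 43 parents would be missed.** The figure counts expected high scorers. Parents already high at T1 are scored face-to-face and given resource information then. The added exposure is new or worsening scores between visits, which the documents do not let us estimate.

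The reply does not supply the missing step. The breadth of the rule means the duty extends to T2, yet it depends on a score being noted, and nothing says how a T2 score comes to be noted.

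**Conclusion.** The point holds in a limited form. The stated T2 collection mode and the stated CES-D safety procedure do not fit together: no passage says who scores the 6-week form, how soon, or by what contact route the parent is reached. Followed as written, the plan allows a high score to stay unread for about six to seven weeks.

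This rests on reading the CES-D as part of the emailed survey, which follows from the SF-12 being the only instrument given to the phone. It does not depend on the count. The figure of about 43 of 111 only shows that high scores would be common if a rate observed in mothers carried over to a sample that includes 24 fathers. It also includes scores of exactly 16, whereas the notification rule applies to scores above 16. The point needs correcting because the procedure protects participants and the repair is small.

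**What to change.** Reconcile the Research Design paragraph, the procedures text after Table 1, item 2 of Study Design, Procedures and Timeline, and the matching text under Risks to Research Participants. Together they should state, for T2, who sees the CES-D score, within what time, and by what route the parent is contacted.

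One way is to have REDCap compute the CES-D total on submission and alert study staff, who then apply the procedure already in the plan by phone. This keeps the CES-D self-administered at all four time points. The cost is minor REDCap set-up, staff time to monitor alerts, and a few sentences of protocol text.

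Moving the CES-D into the SF-12 call would also put the score in front of staff. However, it would make an Aim 1 outcome interviewer-administered at one time point only, adding a mode difference to the longitudinal analysis, so the alert is preferable on statistical grounds.

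The same edit should reconcile the treatment of a score of exactly 16, which counts as high in the Background but does not trigger notification in the procedures text. Which thresholds and clinical actions apply is for the sponsor and the investigator to settle.
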